Therapy with (Li-ESWT) for erectile dysfunction has been proposed as a new alternative in the management of erectile dysfunction (12, 22-25). Its mechanisms of action can be multiple, but are summarized in the increase in vascular flow to the corpora cavernosa generated by a process of neovascularization (26) secondary to angiogenesis promoted by endothelial growth factors such as vascular endothelial growth factor (VEGF), endothelial cell growth factors and cell proliferation nuclear antigen (27), in addition to the increase in the concentration of vasodilator substances such as nitric oxide. The therapy with Li-ESWT has been presented as a therapeutic option, which does not replace the other alternatives, but which adds efficacy to traditional ED management (28).

Likewise, therapy with radial waves arises as a new option for the management of this disease, which has been conducted by different specialists given the benefit shown in the increase of blood flow and muscle recovery for different musculoskeletal conditions. However, currently there are no controlled studies that report on the efficacy and safety of this therapy for the treatment of erectile dysfunction (16, 17). For this reason, it is pertinent to carry out a clinical trial that allows obtaining valid results and thus making reliable clinical decisions.

Objectives

Primary

To evaluate the effectiveness of radial shock wave therapy in patients with moderate erectile dysfunction ² measured as the increase in the average IIFE-EF score at the end of the treatment.

Secondary

- 1. To evaluate the effectiveness of radial shock wave therapy at one month of follow-up, with respect to the change in the average IIFE-EF score.
- 2. To evaluate the efficacy of radial shock wave therapy with respect to the average score of the erection hardness scale (EHS), at the end of the treatment and at one month of follow-up, in the intervention and control groups.
- 3. To evaluate the effectiveness of radial shockwave therapy, regarding the change in the use of sildenafil at the end of treatment and at one month of follow-up, in the intervention and control groups.
- 4. To compare the incidence of adverse events in the intervention and control groups.

² For this study moderate erectile dysfunction is considered a score on the IIEF-EF scale from 11 to 21, which includes the mild to moderate and moderate categories.

Materials and methods

Type of study

Randomized, double-blind clinical trial.

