Interventions

Each patient will be assigned randomly to one of the following groups:

- Arm 1 (Radial wave therapy + oral treatment): 6 radial waves' sessions. A weekly session of radial waves will be applied with the following parameters: 6000 pulses at 1.5-2.6 bar (depending on patient tolerance), with a frequency of 17Hz, the frequency should increase to 22HZ the first 500 impulses to create mild anesthesia in the area; in all the sessions of radial waves, 4000 impulses will be distributed in the body of the penis in scanning technique and 2000 impulses in the perineal area, specifically in the ischiocavernosus and bilateral bulbo-sponge muscles. During the period of therapy application, patients will receive oral treatment with sildenafil 4 according to the patient's degree of affectation.
- Arm 2 (Placebo therapy + oral treatment): 6 sessions of placebo therapy. There will be a weekly session of placebo wave therapy, using the respective device to prevent the patient from receiving the radial wave. The same parameters of the "real" therapy will be used: 6000 pulses at 2.6 bar, with a frequency of 17 Hz; in all the sessions of radial waves, 4000 impulses will be distributed in the body of the penis in scanning technique and 2000 impulses in the perineal area. During the period of therapy application, patients will receive oral treatment with sildenafil 5 according to the patient's degree of affectation.

The radial waves will be administered with the Masterpuls MP50 device from Storz medical.

Primary Outcome

The primary outcome of this study is the difference in the average score of the IIEF-EF scale (Annex 3) in at least 5 points at the end of the treatment.

Secondary outcomes

- IIEF-EF score after one month of follow-up.
- Erection Hardness Score (EHS) at the end of treatment and one month follow-up: The EHS is a unique Likert scale and the version validated in Spanish (35) will be used, which has the following score, 0: The penis does not change in size or hardness; 1: The penis increases in size but does

⁴ This is the standard treatment.

⁵ This is the standard treatment

not become rigid; 2: The penis is rigid but not enough to penetrate; 3: The penis is rigid enough for penetration but not completely hard; and 4: The penis is completely hard or rigid (Annex 4).

- Change in the dose or use of sildenafil.
- Incidence of adverse events.

Safety

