The research subjects will be followed up one month after the end of the treatment. In the event that the patient cannot attend the follow-up, the respective scales will be sent to his e-mail so he can process them and return them by the same means; if after 3 days no response is received, a research assistant will call him and apply the questionnaires by telephone.

Statistical Analysis

A descriptive analysis of the individuals' baseline characteristics linked to each treatment arm will be made, estimating measures of central tendency and dispersion in the case of continuous variables, and measures of relative and absolute frequency for categorical variables.

To evaluate the effectiveness of the therapy, the change in the IIEF-EF scale will be compared at the end of the treatment with the baseline score for each of the arms, using parametric tests in case the

data present a normal distribution, or nonparametric tests otherwise. This same analysis will be done for the scores at the one-month follow-up.

For the EHS scale, the change in at least 1 point will be evaluated, in any of the established measurements. The association between the change in the score and the received treatment will be evaluated estimating the relative risk with its respective confidence interval.

The percentage of patients that decrease or discontinue the use of sildenafil in each group will be estimated, comparing the proportion between the groups at the end of the therapy scheme and the month of follow-up, using the Chi-square test.

The incidence of adverse events for each of the intervention groups will be estimated and the value between them will be compared using the Chi-square test.

In addition to the comparison between groups, stratified analyzes will be performed with multivariate regression models to determine how each intervention adjusted for covariates, such as comorbidities or additional treatments.

An interim analysis will be done once 60% of the total number of patients has completed the treatment (main outcome).

Expected impact

The main contribution of this study is for the scientific community and for patients with erectile dysfunction, by collecting scientific evidence of quality that allows to make a decision about the use of radial waves for the management of erectile dysfunction.

Ethical aspects

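### The only analysis sentence for IIEF-EF, the primary outcome, compares with baseline within each arm and specifies no between-arm test, estimate or confidence interval

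*Combined protocol and SAP*

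**What the plan says.** **Analysis.** For IIEF-EF, the Statistical Analysis section says that "the change in the IIEF-EF scale will be compared at the end of the treatment with the baseline score for each of the arms", by parametric tests if the data are normal and nonparametric tests if not. No test is named. For the secondary time point it adds: "This same analysis will be done for the scores at the one-month follow-up". The other three outcomes in that section each get a between-arm analysis: a relative risk with confidence interval for EHS, and a Chi-square test for sildenafil use and for adverse events.

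**Objectives and outcomes.** The primary objective is "measured as the increase in the average IIFE-EF score at the end of the treatment". Secondary objective 1 is worded "with respect to the change in the average IIFE-EF score". Neither names a comparator. Secondary objectives 2 to 4 do refer to both groups, for example "at the end of the treatment and at one month of follow-up, in the intervention and control groups". The primary outcome is "the difference in the average score of the IIEF-EF scale (Annex 3) in at least 5 points at the end of the treatment", without saying between which groups or times. The secondary outcome is simply "IIEF-EF score after one month of follow-up".

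**Evidence of a between-arm intent.** Under Research hypothesis, the null sets the change on radial waves equal to that on placebo, and the alternative asks for at least five points more. The Sample size section powers an additional 5 points over a 5-point change on control. The procedures section makes later treatment of placebo patients depend on a difference between the two therapies. The Statistical Analysis section itself says "In addition to the comparison between groups, stratified analyzes will be performed with multivariate regression models".

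**The concern.** The hypothesis is about a difference between arms, but the sentence that should test it names the baseline score as comparator, arm by arm. A pre/post test in the radial-wave arm credits radial waves with everything that changes over the treatment period, including the response to sildenafil and to the placebo procedure. The plan itself puts that background change at 5 points.

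The primary outcome wording does not settle the matter. If its 5 points are counted from baseline, the change expected on control would already meet the criterion.

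If the sentence is instead read as a between-arm comparison, the reader still cannot tell what the primary result will be. The plan does not name the test or the effect measure and does not promise a confidence interval.

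**Working it through.** **Inputs from the Sample size section.** Control change 5 points; additional change 5 points; SD 8; 33 evaluable patients per group; power 80%. The one-tailed level given as 97.5% is read as one-sided 0.025, with 0.05 also shown. The plan does not say whether 8 is the SD of the score or of the change. It is taken as the SD of change, with 5 to 10 as the range.

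**1. The plan's own figure.** For two independent means, n per group = 2 × SD² × (z_alpha + z_power)² / difference².
- One-sided 0.025: 2 × 64 × (1.960 + 0.842)² / 25 = 40.2, so 41 (42 with the t distribution).
- One-sided 0.05: 2 × 64 × (1.645 + 0.842)² / 25 = 31.7, so 32 (33 with the t distribution).

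The stated 33 is therefore a two-sample calculation that is reproduced at one-sided 0.05. The mismatch with the stated level is a separate matter. What counts here is that the trial was sized for a comparison of arms.

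**2. The sentence taken literally, with no radial-wave effect.** The radial-wave arm then changes by the same 5 points as control. For a one-sample t-test on change, the noncentrality is 5 / (SD / √33) on 32 df. The critical value is 2.037 at 0.025 and 1.694 at 0.05.

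| SD of change | Noncentrality | Significant at 0.025 | Significant at 0.05 |
|---|---|---|---|
| 5 | 5.745 | over 99.9% | over 99.9% |
| 8 | 3.590 | 93.6% | 96.9% |
| 10 | 2.872 | 79.5% | 87.8% |

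**3. The between-arm reading, with no effect.** A single fixed test errs 2.5% of the time. The open choice was simulated with 20,000 trials per setting, 33 per arm, baseline uniform on 11 to 21, normal errors, SD 5, 8 or 10, and baseline-to-end correlation 0, 0.3 or 0.5.
- t-test or rank test on change, chosen by a normality test: about 2.5–2.6%. The plan names no normality test, so Shapiro-Wilk at 0.05 in each arm is an assumption.
- The more favourable of the two tests always reported: about 2.8–3.1%.

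**4. What baseline adjustment adds.** For a true difference of 5 at SD 8, the unadjusted two-sample t-test has noncentrality 5 / (8 × √(2/33)) = 2.539 on 64 df, giving power 70.6% at one-sided 0.025.

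For ANCOVA, assume baseline SD √10 = 3.16 (uniform on the integers 11 to 21). The end-score SD s1 solves 64 = 10 + s1² − 2 × r × 3.16 × s1, where r is the baseline-to-end correlation, and the residual SD is s1 × √(1 − r²). With 63 df:

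| r | Residual SD | Power at 0.025 |
|---|---|---|
| 0 | 7.35 | 77.7% |
| 0.2 | 7.85 | 72.2% |
| 0.3 | 7.97 | 70.8% |
| 0.4 | 7.99 | 70.6% |
| 0.5 | 7.88 | 71.9% |

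The gain is zero to modest.

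**The case against.** The between-arm contrast is stated in the hypotheses, the sample size and the procedures, and the analysis section presupposes a comparison of groups. The English is rough, and a change cannot sensibly be compared with a baseline score. The sentence may simply mean that change from baseline is compared across the arms. No passage says that efficacy would be declared from one arm's pre/post test. This stands: the 94% belongs only to the literal wording and does not forecast how the trial will be analysed.

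It is also fair that the choice between parametric and nonparametric tests, made on normality, does little to the error rate. A reader might infer a larger inflation by letting the analyst pick the best of five tests (t and rank on change, t and rank on end score, ANCOVA). Simulation gives 3.9–4.7% for that. But it requires selective reporting across tests that the plan does not list. The hypotheses and the analysis sentence both point to change, and the covariate models are described as additional.

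ANCOVA is not the only cure; a named two-sample test on change with a confidence interval would also close the gap.

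What the objection does not supply is the test. The phrase about comparing groups names no outcome, method or estimate, and intent stated elsewhere does not make a primary analysis specified.

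**Conclusion.** The point holds as a failure of specification. The primary IIEF-EF analysis, and its repeat at one month, has no stated between-arm test, estimate or confidence interval, and the sentence as written does not test the null hypothesis.

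Followed literally, it would give a significant result in the radial-wave arm about 94% of the time with no radial-wave effect. That rests on SD 8 being the SD of change (80% at SD 10, over 99.9% at SD 5), 33 per arm, a 5-point control change and one-sided 0.025. On the intended reading, error is at most about 3% against 2.5% for a t-test or rank test on change, under normal errors.

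Two stronger readings are not supported. The documents do not show that the trial will be judged on change from baseline alone, since its hypotheses and sample size say otherwise. Nor do they show large error inflation from the open choice of test. The point must still be fixed, because a confirmatory trial needs its primary test named before the data are seen.

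**What to change.** Replace the IIEF-EF sentence with wording such as:

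> The primary analysis is the between-arm difference in mean IIEF-EF at the end of treatment, estimated by ANCOVA with arm and baseline IIEF-EF, with a confidence interval. The same model is used at one month. Within-arm changes are descriptive only.

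This also removes the choice of test by normality. Add *between arms* to the primary objective, to secondary objective 1 and to the primary outcome, so that all of them match the hypotheses.

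The cost is wording only. Baseline IIEF-EF is already collected, so no data or patients are added. The main gain is one pre-fixed test of the null hypothesis; any gain in power is zero to modest. The definition of the patients analysed and any adjustment for the interim analysis are separate matters that this change does not settle.

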Research hypothesis

Ho: The change in the score of the IIEF-EF scale in patients with moderate erectile dysfunction³, treated with radial wave therapy, is equal to those who receive placebo therapy.

Ha: The change in the score of the IIEF-EF scale increases at least five points in patients with moderate erectile dysfunction treated with radial wave therapy, compared with the score of patients receiving placebo therapy.

Study population

Patients diagnosed with erectile dysfunction of vascular origin who are treated at the Boston Medical Group facilities in Bogotá.

Inclusion criteria

- 1. Men older than 18 years
- 2. Erectile dysfunction presents for more than 3 months in more than 50% of intercourse.
- 3. IIEF-EF score between 11 and 21.
- 4. Patient who agrees to enter the study through the signing of an informed consent.

Exclusion criteria

- 1. EHS score of 4
- 2. Bladder, prostate or colon cancer.
- 3. Patients with ED of psychological origin.
- 4. Patients with spinal cord injury.
- 5. Patients with anticoagulant use.
- 6. Patients with sickle cell anemia.
- 7. Patients with clinical suspicion of hypogonadism (AMS greater than 36, Annex 1).
- 8. Patients with infections or active lesions of the penis or pubic area.
- 9. Patients with ED secondary to drug treatment (antiandrogenic therapy, antidepressants, use of corticosteroids, antiparkinsonians, antipsychotics).
- 10. Radical prostatectomy or other radical pelvic surgery.
- 11. Antecedents of pelvic radiotherapy.
- 12. Patients with penile implant.
- 13. Endocrine diseases that occur with ED: acromegaly, gigantism, Addison's disease, hyperprolactinemia, androgenic deficiency.
- 14. Patients with neurological diseases (Parkinson's, CVD, dementia of any origin)

³ For this study moderate erectile dysfunction is considered a score on the IIEF-EF scale from 11 to 21, which includes the mild to moderate and moderate categories.

Sample size

Assuming that the placebo plus drug group has an average change in the score of the IFE-EF scale of 5 points and that the new wave therapy must have an additional change of at least 5 points to be considered clinically relevant, for a power of 80% and a one-tailed level of significance of 97.5%, with a standard deviation of 8 points, a sample size of 33 patients was estimated for each group. Adjusting for a percentage of losses of 20%, the size per group is 40 patients, for a total of 80 patients in the study. These calculations were performed in Stata 15.1®.

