It will be determined by the presence of adverse events. These will be evaluated at the end of each of the therapies and a month of follow-up. This variable will be dichotomous as the presence or absence of adverse events. Additionally the type of adverse event and the degree of severity will be recorded.

Randomization

The assignment of patients to the treatment arms will be done with the method of randomization by balanced blocks of unequal cells. The assignment of the treatment will be centralized, so once the patient agrees to participate in the study and signs the informed consent, an email should be sent to the research center ([contact]) who will only inform the therapist which is the group (intervention or control) that corresponds to the patient.

To conceal the assignment sealed opaque envelopes will be used, this envelope will be opened once the request is generated in each center, after the patient has voluntarily accepted to participate in the study and the informed consent process has been carried out with signature of the written document.

Neither the patient, the attending physician, nor the professional who applies the questionnaires will know the group to which the patient was assigned.

Techniques, procedures, data collection and processing

The subjects who attend consultation for erectile dysfunction at the Boston Medical Group clinics in Bogotá (Colombia) and Lima (Peru), will be treated as usual according to the institutional management protocols and screened to determine if they meet the eligibility criteria. If so, they will be invited to participate in the research project and the informed consent process will be carried out in which the objectives, risks, benefits, procedures and other relevant research data will be explained.

Once the patient has voluntarily accepted to participate in the study and the informed consent document has been signed, an email will be generated to the research center to request the group to which the patient will be assigned.

A baseline measurement of the IIEF-EF and the EHS will be made before starting the intervention; In addition, the AMS questionnaire should be completed to rule out hypogonadism. Once the treatment is completed, patients must complete the IIEF-EF and EHS scales in the last treatment session. In this same session, the patient will be evaluated for adverse events; later, they will have

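### The primary IIEF-EF comparison is an unadjusted change score; naming baseline IIEF-EF as a covariate is a free improvement with a modest expected gain

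*Combined protocol and SAP*

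**What the plan says.** The Statistical Analysis section states that "the change in the IIEF-EF scale will be compared at the end of the treatment with the baseline score for each of the arms". The test is parametric if the data look normal and nonparametric if not, and the one-month scores are handled the same way. The hypotheses (Research hypothesis) and the Sample size section are also framed in terms of change.

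The baseline score is available. Under Techniques, procedures, data collection and processing, "A baseline measurement of the IIEF-EF and the EHS will be made before starting the intervention". The Randomization section describes blocks and mentions no stratification by baseline score.

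The Statistical Analysis section later adds regression models on top of the between-group comparison, "adjusted for covariates, such as comorbidities or additional treatments". Baseline IIEF-EF is not among the examples.

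**The concern.** A comparison of raw change is a model in which each extra baseline point is worth exactly one extra point at the end of treatment. For a noisy score in men selected on that score (11 to 21 at entry), the usual expectation is a slope below 1, because low scorers tend to move up more than high scorers. Change then remains correlated with baseline, with two consequences. The contrast carries variance that a baseline covariate would remove, and any chance difference in baseline severity between the arms passes partly into the estimated effect.

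The trial is small: 80 men, with 20% losses allowed for. Adding baseline after the data are seen would look selective; specifying it beforehand would not.

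**Working it through.** **Inputs from the Sample size section.** Difference in mean change 5 points; SD "with a standard deviation of 8 points", which I read as the SD of change because the text does not say what it refers to; 33 men per arm before losses; "for a power of 80% and a one-tailed level of significance of 97.5"%, which I read as one-sided alpha 0.025.

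**Assumptions, not in the documents.** Baseline SD (SD0) = 3.16, the value for whole-number scores spread evenly over 11 to 21, since √((11² − 1)/12) = √10. Slope b of final score on baseline from 0 to 1.

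**The plan's own figure.** A two-sample t calculation with difference 5, SD 8 and 80% power gives 42 per arm at one-sided 0.025 (41 by the normal approximation). It gives 33 at one-sided 0.05. So 33 is not reproduced at the stated level. At 33 per arm the unadjusted comparison has power 70.6% at one-sided 0.025 and 80.7% at one-sided 0.05 (noncentral t, 64 degrees of freedom). This mismatch is a separate matter. I use 0.025 below because it is the level stated.

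**Variance removed by adjustment.** Change = final − baseline, so its slope on baseline is b − 1. Residual variance after adjustment = 64 − (1 − b)² × SD0². Proportion removed = (1 − b)² × 10/64.

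- b = 1: 0
- b = 0.5: 0.25 × 10/64 = 3.9%; residual SD 7.84
- b = 0.25: 0.5625 × 10/64 = 8.8%; residual SD 7.64
- b = 0: 10/64 = 15.6%; residual SD 7.35

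**Power at 33 per arm, one-sided 0.025.** Noncentrality = 5 / (residual SD × √(2/33)), with 63 degrees of freedom once baseline is in the model. The last column is 33 / (1 − proportion removed).

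| Slope b | Variance removed | Power, unadjusted | Power, adjusted | 33 men act like |
|---|---|---|---|---|
| 1 | 0% | 70.6% | 70.5% | 33.0 |
| 0.5 | 3.9% | 70.6% | 72.2% | 34.3 |
| 0.25 | 8.8% | 70.6% | 74.5% | 36.2 |
| 0 | 15.6% | 70.6% | 77.7% | 39.1 |

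The formula ignores the small cost of estimating the slope; a simulation at b = 0 gave 77.3%. With these inputs b = 0.5 corresponds to a baseline-to-final correlation of about 0.20, b = 0.25 to about 0.10, and b = 0 to none.

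**Sensitivity to the baseline SD.** At SD0 = 2.5 the proportion removed is 2.4% (b = 0.5) to 9.8% (b = 0). At SD0 = 5, the largest value that a range of 11 to 21 allows, it is 9.8% to 39%. That extreme needs half the men at 11 and half at 21.

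**Chance imbalance.** SD of the between-arm baseline difference = 3.16 × √(2/33) = 0.78 points, so a two-SD imbalance is about 1.6 points. The unadjusted contrast moves by (1 − b) times this: about 0.8 points at b = 0.5, 1.6 at b = 0 and nothing at b = 1. For scale, the target is 5 points and the standard error of the unadjusted contrast is 8 × √(2/33) = 1.97 points.

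**The case against.** The strongest reply is that little is at stake. The entry window restricts the baseline spread, so baseline can explain only a small part of an SD of 8. At slope 0.5 the gain is about 1.3 men per arm, and the documents give no slope. That stands, and it limits the point to an efficiency improvement.

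Four stronger readings are tempting, and the documents do not support them.

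- A reader might infer that the imbalance biases the trial. Under randomisation the change-score contrast is unbiased and its test keeps its error rate. Chance imbalance is already part of the 1.97-point standard error. The 0.8 to 1.6 points describe conditional imprecision in an unlucky trial (a two-SD imbalance arises in roughly 1 in 20), and they are smaller than one standard error. Baseline characteristics are to be tabulated by arm, so an imbalance would be visible.
- A reader might infer that the plan rules out baseline adjustment. The covariate list for the supplementary regressions is illustrative. Baseline IIEF-EF is unspecified there, not excluded. What stands is that those models are additional, the primary result stays unadjusted, and an open list leaves the covariates to be chosen later.
- A reader might apply the textbook variance ratio (1 + correlation)/2. It assumes equal variances at both times. With an SD of change of 8 and a non-negative correlation, that needs a baseline SD of at least 8/√2 = 5.66, above the maximum of 5 that the entry range permits.
- A reader might expect adjustment to make up for 33 per arm falling short of the 42 needed at one-sided 0.025. At SD0 = 3.16 even slope 0 leaves power at 77.7%.

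It can also be said that the quoted sentence reads literally as a within-arm comparison with baseline. The hypotheses and the later reference to a comparison between groups show that a between-arm test is meant, but the wording is loose. Baseline is not a covariate under either reading.

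**Conclusion.** The point holds as a free improvement. The primary IIEF-EF analysis is an unadjusted comparison of change, with the type of test left to the data, and the baseline score already collected is not specified as a covariate. With 8 taken as the SD of change, 33 men per arm and an assumed baseline SD of about 3.16, the gain in power at one-sided 0.025 is 1.6 percentage points at slope 0.5 (72.2 − 70.6), 3.9 at 0.25 and 7.1 at 0. At slope 1 it is a loss of 0.1. The slope is unknown, so the size of the gain within this range cannot be settled from the documents. The case for acting is that the downside is negligible and that the model also replaces an unnamed, data-dependent test with one defined estimate. The planned analysis is not invalid.

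**What to change.** Replace the effectiveness sentence in the Statistical Analysis section with wording such as: the primary analysis is a between-arm linear model (ANCOVA) of end-of-treatment IIEF-EF on treatment arm and baseline IIEF-EF, reported as the adjusted mean difference with its confidence interval; the same model is used for the one-month score; a rank-based test is reported as a sensitivity analysis and does not replace the primary model on the basis of a normality check.

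The new sentence should say explicitly that the comparison is between arms, which also removes the within-arm reading.

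The change is confined to IIEF-EF. The plan states a relative risk for EHS and this point does not touch it. The cost is a short rewrite of the plan and one degree of freedom, with no new data, patients or procedures.

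### The IIEF-EF test is chosen from the observed distribution, and its rank-test branch gives no estimate to set against the 5-point mean difference on which the trial is built

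*Combined protocol and SAP*

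**What the plan says.** The Statistical Analysis section states that "the change in the IIEF-EF scale will be compared at the end of the treatment with the baseline score for each of the arms". The choice of method is left to the outcome data: a parametric method applies if the "data present a normal distribution, or nonparametric tests otherwise". For the later visit it adds: "This same analysis will be done for the scores at the one-month follow-up". It does not say which parametric or nonparametric test is meant, how normality is judged, or whether it is judged on pooled data, by arm or on residuals. No effect measure or interval is promised for IIEF-EF, although the same section promises a relative risk with its interval for EHS.

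The rest of the plan is stated in mean points:
- Objectives: effectiveness is "measured as the increase in the average IIFE-EF score at the end of the treatment".
- Primary Outcome: "the difference in the average score of the IIEF-EF scale", with a threshold of 5 points.
- Sample size: the new therapy needs "an additional change of at least 5 points to be considered clinically relevant", with a standard deviation of 8.

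Baseline IIEF-EF is available for everyone: "A baseline measurement of the IIEF-EF and the EHS will be made before starting the intervention". Regression models with covariates are planned, but in addition to the group comparison. Baseline IIEF-EF is not among the covariates given as examples.

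**The concern.** A comparison of means and a rank test answer different questions. The first estimates the difference in average change. The second asks whether one arm's values tend to be larger than the other's. Under this rule, the outcome data decide which question the trial answers, through a criterion that is not written down. If the data look non-normal, the named analysis yields a p-value but no number to hold against the 5-point criterion, and no interval for it. The one-month result inherits the problem, and the two visits could end on different types of test.

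The words about each of the arms add a second looseness, since they can be read as a before-after test within each arm. The hypotheses, and the later reference to a comparison between groups, point to a between-arm analysis. The plan should say so.

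**Working it through.** **Inputs from the plan.** Control change 5, additional change 5, SD 8, power 80%, one-tailed 97.5% (read as one-sided 0.025), 33 evaluable and 40 recruited per group (Sample size); baseline 11 to 21 (Inclusion criteria).

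**Assumptions, not in the documents.** Scores range from 1 to 30. Normality is checked by Shapiro-Wilk at 0.05 in each arm, with a switch to Mann-Whitney if either arm fails.

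**1. The plan's own figure.** n per group = 2 × (z_α + z_power)² × SD² / difference².
- One-sided 0.025: 2 × (1.960 + 0.842)² × 64 / 25 = 40.2, so 41 (42 with the t distribution).
- One-sided 0.05: 2 × (1.645 + 0.842)² × 64 / 25 = 31.7, so 32 (33 with t).

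The stated 33 is reproduced only at one-sided 0.05. That is a separate matter, but it sets the reference power used here.

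**2. Rank test under a pure shift.** Power from the noncentral t, with n multiplied by the rank test's asymptotic relative efficiency (difference 5, SD 8, one-sided 0.025):

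| | 33 per group | 40 per group |
|---|---|---|
| Test of means | 70.6% | 78.8% |
| Rank test, normal data (0.955) | 68.5% | 76.9% |
| Rank test, least favourable shape (0.864) | 64.0% | 72.6% |

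The loss is about 2 points for normal data and at most 70.6 − 64.0 = 6.6 points. In simulation at 33 per group the rank test did better with skewed changes (exponential, 93% against 71%) and with heavy tails (t with 3 df, 91% against 76%).

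**3. How often the rule switches.** With uncapped normal data, about 9% of simulated trials. With scores capped and the plan's inputs, 48% to 57%. With the underlying shift enlarged so that the observed difference stays close to 5 (4.87 at 33 per group), 54.8% at 33 and 66.1% at 40.

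**4. Power of the rule with capped scores.** Under the plan's inputs at 33 per group, the test of means had 64% and the rule 65%. With the enlarged shift, both had 88.0%.

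**5. Responder subgroups, 33 per arm.** Power of a test of means, then of the rule:

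| Active-arm responders | Within-group SD | Uncapped | Capped at 30 |
|---|---|---|---|
| 25% gain 20 extra | 3 | 87% vs 42% | 60% vs 46% |
| 33% gain 15 extra | 3 | 94% vs 65% | 80% vs 70% |
| 25% gain 20 extra | 5 | 73% vs 43-44% | 38% vs 37% |
| 33% gain 15 extra | 5 | 81% vs 73% | 56% vs 56% |
| 25% gain 20 extra | 8 (plan) | – | 25% vs 28% |
| 33% gain 15 extra | 8 (plan) | – | 34% vs 37% |

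The uncapped rows are extreme cases. With the 5-point control change, responders gain 5 + 20 = 25 or 5 + 15 = 20 points on average. From a baseline of 11 to 21, a maximum of 30 allows only 30 − 21 = 9 to 30 − 11 = 19. Once capped, these scenarios no longer yield a 5-point difference, only about 2.2 to 2.9.

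**6. Type I error.** The rule rejected in 1.7% to 2.8% of null trials, against a nominal one-sided 2.5%. With equal means but deliberately unequal shapes, the two-sided error was about 5% to 7.7%, against 5%.

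**7. Gain from baseline adjustment.** If baseline is uniform over the 11 integers from 11 to 21, its variance is (11² − 1)/12 = 10. Residual variance = 64 − 10 × (slope − 1)².

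| Slope of final on baseline score | Residual variance | Reduction |
|---|---|---|
| 0 | 54.0 | 16% |
| 0.5 | 61.5 | 4% |
| 0.75 | 63.4 | 1% |
| 1 | 64.0 | 0% |

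**The case against.** The rule is common practice and does little harm to validity. Its type I error is close to nominal, and it tends to move to the rank test when that test is competitive or better. Nothing in the plan forbids reporting the mean difference beside a rank test, and Primary Outcome is defined as that difference. Unadjusted change scores are valid under randomization, and the covariate list for the regressions is only illustrative.

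Most of this stands. It answers a charge of invalidity or lost power, but not the present point. A mean difference reported beside a rank p-value would be the analyst's choice after seeing the data, with no stated interval. A Hodges-Lehmann shift could accompany the rank test, but the plan does not call for one, and in general it matches the mean difference only under a pure shift. The regressions are additional and name no primary estimate.

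A reader might go further and infer that the rule could cost the trial much of its power. The documents do not support that. Losses of 30 points or more appear only in uncapped scenarios with gains that the entry range and an assumed maximum of 30 rule out, and with a within-group SD below the plan's 8. It would also be wrong to say that the plan specifies a preliminary normality test. It names none, and Shapiro-Wilk is an assumption made here to put figures on the rule.

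**Conclusion.** The point holds as a gap in pre-specification. The observed distribution settles the primary and one-month IIEF-EF analysis by an unwritten criterion, and one of the two branches does not estimate the 5-point mean difference used in the objective, outcome and sample size. If scores are capped at 30 and normality is checked as assumed, the chance of landing on that branch is about one in two.

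The consequence is an unfixed estimand, not a large loss of power. The rule loses nothing under the plan's own inputs. A rank test loses at most about 7 points under a pure shift. A loss of about 9 to 15 points survives capping only when responses cluster tightly (SD 3). Skewed or heavy-tailed changes favour the rank test. Baseline adjustment adds a modest gain, 0 to 16% of residual variance. This should be fixed, but it is not serious enough to be called essential. The simulated figures depend on the assumed score range and normality check. The mismatch between the rank test and the 5-point criterion does not.

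**What to change.** Replace the rule with one analysis fixed before the outcome data are examined:
- Compare end-of-treatment IIEF-EF between arms by ANCOVA, with treatment and baseline IIEF-EF in the model.
- Report the adjusted mean difference with its confidence interval, using robust standard errors, whatever the distribution, and read it against the 5-point criterion.
- Use the same model for the one-month score.
- Keep Mann-Whitney as a labelled sensitivity analysis only.

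Stating that the comparison is between arms also removes the within-arm reading. The cost is a few sentences of SAP text; no new data are needed, because baseline is already collected. The downside is some loss of power relative to a rank test if changes prove heavy-tailed or strongly skewed (76% against 91%, and 71% against 93%, in the unbounded examples above, for an unadjusted test of means).
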